11.2.2 Gout Flare Assessment

Gout flare will be assessed as part of AE collection with severity determined as described in [Section 12.2.2.3](#). Gout flares will be assessed at each study visit during the Treatment Phase using a validated definition of flares in patients with established gout ([Gaffo 2018](#)). In addition, in an exploratory manner, gout flares will be self-assessed weekly by the patient after randomization and in each Treatment Period using a weekly flare diary ([Poiley 2016](#)).

11.2.3 Joint Assessment

Tender and/or swollen joints will be counted. The following joints will be assessed: metacarpophalangeal, proximal interphalangeal, and distal interphalangeal joints of the hands; the metatarsophalangeal and interphalangeal joints of the feet; shoulder, elbow, wrist, knee, ankle, tarsus, sternoclavicular, and acromioclavicular joints.

11.3 Health Questionnaires: Patient Reported Outcomes and Quality of Life Assessment

11.3.1 Health Assessment Questionnaire-Disability Index (HAQ-DI)

The HAQ-DI will be administered according to the schedule described in [Appendix A](#).

The HAQ-DI is an instrument that assesses fine movements of the upper extremity, locomotor activities of the lower extremity, and activities that involve both the upper and lower extremities. Standard scoring takes into account the use of aids and devices or assistance from another person. There are 20 items in 8 categories that represent a comprehensive set of functional activities: dressing, rising, eating, walking, hygiene, reach, grip, and usual activities. The stem of each item assesses a patient's functional ability using their usual equipment during the past week. Each category contains at least 2 specific sub-category questions. For example, under the category "walking," patients are asked about their ability to walk outdoors on flat ground and to climb up 5 steps. The HAQ-DI includes a patient global assessment of disease and a visual analog scale for pain assessment.

11.3.2 Provider Global Assessment of Disease Activity

The Provider Global Assessment of Disease Activity (PrGA) will be conducted according to the schedule described in [Appendix A](#). The PrGA will be administered to assess the severity of the patient's disease on a scale from 0 (patients feels "very well") to 100 (patient feels "very poor"). Lower scores indicate less severe disease.

11.3.3 Short Form Health Survey 36 (SF-36)

The SF-36 will be administered according to the schedule described in [Appendix A](#).

The SF-36 is a 36-item scale constructed to survey health status and quality of life ([Ware 1992](#)). The SF-36 assesses 8 health concepts: limitations in physical activities because of health problems; limitations in social activities because of physical or emotional problems; limitations in usual role activities because of physical health problems; bodily pain; general mental health (psychological distress and well-being); limitations in usual role activities because of emotional problems; vitality (energy and fatigue); and general health perceptions. The standard form of the instruments asks for patients to reply to questions according to how they have felt over the previous week.

11.4 Inflammation Biomarker and Multiomic Assessments

11.4.1 Inflammation Biomarkers of Gout

Blood samples will be drawn according to the schedule described in [Appendix A](#) for assessment of inflammation biomarkers. Validated methods will be used for processing samples and for measurement of inflammation biomarkers as described in the Study Operations Manual.

11.4.2 Multiomic Markers of Gout

A blood sample will be drawn according to the schedule described in [Appendix A](#) for determination of correlations between multiomic markers of gout and observed treatment effect of study drug. Validated methods will be used for processing samples and for measurement of multiomic markers as described in the Study Operations Manual.

11.4.3 Biomarkers of Immune Tolerance

Blood samples will be drawn according to the schedule described in [Appendix A](#) for assessment of inflammation biomarkers. Validated methods will be used for processing samples and for measurement of inflammation biomarkers as described in the Study Operations Manual.

11.4.4 Multiomic Markers Related to Immune Tolerance

A blood sample will be drawn according to the schedule in [\(Appendix A\)](#) for determination of correlations between multiomic markers of gout and observed treatment effect of study drug. Validated methods will be used for processing samples and for measurement of multiomic markers as described in the Study Operations Manual.

11.4.5 Human Leukocyte Antigen (HLA) Typing

A blood sample will be drawn according to the schedule described in [Appendix A](#) for determination of human leukocyte antigen (HLA). If the sampling timepoint has passed, then the sample for HLA typing should be drawn at the next scheduled study visit. Validated methods will be used for processing samples and for measurement of human leukocyte antigen as described in the Study Operations Manual.

11.4.6 Imaging Assessments

Multi-energy computed tomography (CT) scans will be performed at selected investigational sites as an exploratory measure to visualize monosodium urate crystal deposits and/or total body monosodium urate crystal deposits. Imaging will be conducted according to the schedule described in [Appendix A](#). The Screening assessment should be performed after preliminary determination of eligibility ([Section 8](#)) and prior to the first study drug dose on Day 0 of Treatment Period 1. Procedures for the multi-energy CT scan and analysis can be found in the Study Operations Manual.

12. ASSESSMENT OF SAFETY**12.1 Safety Parameters****12.1.1 Demographic/Medical History**

Demographic and significant medical history will be documented according to the schedule described in [Appendix A](#). Medical history will be recorded up to the time of dosing.

12.1.2 Concomitant Medications and Procedures

Concomitant medications and procedures will be documented according to the schedule described in [Appendix A](#).

12.1.3 Vital Signs

Vital signs will be documented according to the schedule described in [Appendix A](#).

Vital signs will include systolic blood pressure (mmHg), diastolic blood pressure (mmHg), pulse (beats per minute, bpm), respiratory rate (breaths per minute), and temperature (°C). Blood pressure and heart rate will be recorded after at least 5 minutes of rest in a sitting position. The blood pressure measurement should be repeated after at least 30 seconds and the average of the 2 readings calculated and recorded.

12.1.4 Electrocardiogram (ECG)

A standard 12-lead ECG will be performed according to the schedule described in [Appendix A](#).

12.1.5 Weight and Height

Weight (kg) and height (cm) will be performed according to the schedule described in [Appendix A](#). Height will be measured at Screening only. Weight will be used to calculate study drug dosage as described in [Section 10.4](#).

12.1.6 Physical Examination

Physical examinations will be conducted according to the schedule described in [Appendix A](#). Breast, rectal, and urogenital exams are not required unless warranted based on the clinical judgment of the patient's medical history or current medical condition. The physical exam should be done by a physician or physician's assistant or similarly qualified individual. At some visits a Directed Physical Examination will be performed. These exams will be focused on assessment of any patient complaints and concerns.

12.1.7 Chest X-ray

Chest X-rays (CXR) will be performed according to the schedule described in [Appendix A](#). [Post-baseline CXRs will be taken](#) to assess for presence of or changes in interstitial lung disease (ILD) compared to baseline CXR.

12.1.8 Laboratory Assessments

All laboratory assessment will be conducted according to the schedule described in [Appendix A](#). Procedures for processing samples are included in the Study Operations Manual.

12.1.8.1 Hematology

Hematology assessments will include white blood cells (WBC) count with differential, red blood cell (RBC) count, hematocrit (Hct), hemoglobin (Hgb), and platelet (Plt) count.

12.1.8.2 Blood Chemistry

Clinical chemistry assessments will include alkaline phosphatase, alanine aminotransferase (ALT), aspartate aminotransferase (AST), total bilirubin, blood urea nitrogen (BUN), creatinine, fibrinogen, glucose (fasting), and electrolytes (sodium, potassium, chloride, bicarbonate, phosphate, and magnesium), and urine for urine-albumin-creatinine ratio (UACR). If the UACR cannot be calculated due to the microalbumin analysis being below the limit of quantification for the analytical method (eg. <12 mg/dL), the low microalbumin can be used as a surrogate for an acceptable UACR.

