8.2 Patient Exclusion Criteria

A patient who meets any of the following criteria will be excluded from this study:

1. Has a history of anaphylaxis, severe allergic reactions, or severe atopy;
2. Has a history of any allergy to pegylated products, including, but not limited to pegloticase (Krystexxa®), peginterferon alfa-2a (Pegasys®), peginterferon alfa-2b (PegIntron®), pegfilgrastim (Neulasta®), pegaptanib (Macugen®), pegaspargase (Oncaspar®), pegademase (Adagen®), peg-epoetin beta (Mircera®), pegvisomant (Somavert®) certolizumab pegol (Cimzia®), naloxegol (Movantik®), peginesatide (Omontys®), and doxorubicin liposome (Doxil®);
3. Is taking and cannot discontinue known major CYP3A4/P-gp inhibitors or major CYP3A4/P-gp inducers at least 14 days before dosing. Patients must remain off these medications for the duration of the study, including natural products such as St. John's Wort or grapefruit juice.

4. Is taking drugs known to interact with rapamycin (sirolimus - Rapamune[®]) such as cyclosporine, diltiazem, erythromycin, ketoconazole, posaconazole, voriconazole, itraconazole, rifampin, verapamil unless they are stopped 14 days prior to dosing and will not be used/prescribed during the trial.
5. Had major surgery within 3 months of initial screening.
6. Had a gout flare during Screening that was resolved for less than 1 week prior to first treatment with study drug (exclusive of chronic synovitis/arthrits) unless the patient has a history of inter-flare intervals of < 1 week.
7. Has uncontrolled diabetes at Screening with HbA1c \geq 8.5%;
8. Has fasting Screening glucose $>$ 240 mg/dL
9. Has fasting Screening triglyceride $>$ 500 mg/dL;
10. Has fasting Screening low-density lipoprotein (LDL) $>$ 200 mg/dL;
11. Has glucose-6-phosphate dehydrogenase (G6PD) deficiency;
12. Has uncontrolled hypertension defined as blood pressure $>$ 170/100 mmHg at Screening and 1 week prior to dosing
13. Individual laboratory values which are exclusionary
 - o White blood cell count (WBC) $<$ 3.0 $\times 10^9$ /L
 - o Serum aspartate aminotransferase (AST) or alanine amino transferase (ALT) $>$ 3x upper limit of normal (ULN) in the absence of known active liver disease
 - o Estimated glomerular filtration rate (eGFR) $<$ 30 mL/min/1.73 m²
 - o Urine-albumin-creatinine ratio (UACR) $>$ 30 mg/g creatinine (conventional units) or $>$ 3.39 mg/mmol creatinine (SI units)
 - o Hemoglobin (Hgb) $<$ 9 g/dL
 - o Serum phosphate $<$ 2.0 mg/dL

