- Only sites with immediate capability to appropriately respond to a reaction of this severity will be allowed to participate in the trial to reduce the risk to any patient.
- Infusion Reactions (an AESI) will be reported to Parexel Safety in the same manner as SAEs using the same form but ticking the AESI box rather than the SAE box.

Adverse events of special interest (AESI) will be recorded specifically for occurrences of: gout flares, infections, malignancies, viral infections, interstitial lung disease, stomatitis, infusion-related reactions including anaphylaxis, thrombosis (e.g., deep venous thrombosis, pulmonary embolism), and the following laboratory tests, if deemed clinically significant by the PI: hyperlipidemia, worsening of renal function tests, proteinuria, and leukopenia.

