**Statistical Analysis Plan**

Sponsor: Selecta Biosciences

Protocol No.: SEL-212/302

- Glomerular filtration rate (GFR) < 30 mL/min/1.73 m^2
- Urine albumen creatinine ratio (UACR) > 30 mg/g creatinine (conventional units) or > 3.39 mg/mmol creatinine (SI units)
- Hemoglobin (Hgb) < 9 g/dL
- Serum phosphate < 2.0 mg/dL

14. Is receiving ongoing treatment for arrhythmia, including placement of an implantable defibrillator, unless considered stable and on active treatment;

15. Has evidence of unstable cardiovascular disease or unstable cerebrovascular disease. This includes patients who have had a cardiac/vascular event(s) in the last 3 months including heart attack, stroke or vascular bypass prior to dosing or patients who are deemed, by their physician or PI, to have active cardiovascular, cerebrovascular or peripheral vascular symptoms/disease inadequately controlled by medication;

16. Has congestive heart failure, New York Heart Association Class III or IV;

17. Unless clinically stable and/or appropriately treated, electrocardiogram (ECG) with evidence of clinically significant arrhythmia, or other abnormalities that, in the opinion of the investigator, are consistent with significant underlying cardiac disease;

18. History of significant hematological disorders within 5 years or autoimmune disorders, and/or patient is immunosuppressed or immunocompromised;

19. Prior exposure to any experimental or marketed uricase (e.g., rasburicase (Elitek, Fasturtec), pegloticase (Krystexxa®), pegadricase (SEL-037))

20. Patient has received a live virus vaccine in the previous 6 months.

21. Patient is planning to receive any live vaccine during the study. Of note, inactivated vaccines are permitted but, study drug may affect response to vaccination; therefore, during study drug treatment, vaccination with inactivated vaccines may be less effective. Consider high-dose influenza vaccine to increase the likelihood of developing a protective immune response.

22. History of malignancy within the last 5 years other than basal skin cancer;

23. Any condition, that in the opinion of the investigator, would be negatively affected by rapamycin.

24. Patients with a documented history of moderate or severe alcohol or substance use disorder within the 12 months prior to randomization.

25. History of, or evidence of clinically severe, interstitial lung disease

26. Immunocompromised state, regardless of etiology

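### The below-quantification surrogate for UACR (protocol 12.1.8.2, example value 12 mg/dL, no urine creatinine condition) does not guarantee the 30 mg/g limit of exclusion 13

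*Protocol*

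**What the plan says.** Exclusion 13 appears in the protocol synopsis, protocol section 8.2 and SAP section 3.4.2. It excludes a UACR above "30 mg/g creatinine (conventional units") or, equivalently, above "3.39 mg/mmol creatinine (SI units"). The SAP repeats the limit as "Urine albumen creatinine ratio (UACR) > 30 mg/g creatinine (conventional units").

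Protocol section 12.1.8.2 lists the chemistry tests and then deals with a UACR that cannot be calculated because of the albumin result "being below the limit of quantification for the analytical method (eg. <12 mg/dL), the low microalbumin can be used as a surrogate" for an acceptable ratio.

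Three things are absent:

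- The sentence does not refer to urine creatinine.
- It places no ceiling on the limit of quantification.
- It does not say whether it applies only at Screening.

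The exclusion criteria do not mention the surrogate, and neither does the SAP. Sample processing is referred to the Study Operations Manual (protocol 12.1.8), which is not among the documents.

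**The concern.** The exclusion is a limit on a ratio. The surrogate replaces that ratio with its numerator alone. A low albumin concentration shows a low ratio only if the urine is concentrated enough, so whether the surrogate respects the limit depends on two numbers: the laboratory's limit of quantification and the patient's urine creatinine. The protocol gives an example for the first that is high relative to 30 mg/g, and says nothing about the second.

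What is at stake is eligibility, and with it the renal starting point for the safety comparison. UACR is a named safety assessment (protocol 6.2.4). The adverse events of special interest in protocol 12.2.1.5 include these laboratory findings when the investigator judges them clinically significant: "hyperlipidemia, worsening of renal function tests, proteinuria, and leukopenia". Patients who enter above the albuminuria limit, with no baseline ratio on record, would make later proteinuria harder to interpret.

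**Working it through.** **Inputs from the documents**

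- UACR limit: 30 mg/g, also given as 3.39 mg/mmol (protocol synopsis and 8.2; SAP 3.4.2).
- Example limit of quantification for albumin: 12 mg/dL (protocol 12.1.8.2).

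**Inputs not in the documents**

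- Urine creatinine: an assumed illustrative range of 50 to 300 mg/dL, with some values outside it to locate the break-even points.
- Molar mass of creatinine: 113.12 g/mol, a physical constant.

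**Step 1. Is the limit itself consistent?** 30 mg/g × 113.12 g/mol ÷ 1000 = 3.39 mg/mmol. The two units agree, so the limit is not the source of the problem.

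**Step 2. Ratio at the surrogate boundary.** With both concentrations in mg/dL,

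UACR (mg/g) = 1000 × albumin ÷ creatinine.

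An albumin just below the limit of quantification gives a ratio just below 1000 × LOQ ÷ creatinine. That is the largest ratio the surrogate can accept.

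**Step 3. Creatinine needed for the surrogate to guarantee 30 mg/g.** Creatinine ≥ 1000 × LOQ ÷ 30.

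- LOQ 12 mg/dL: 12,000 ÷ 30 = 400 mg/dL.
- LOQ 12 mg/L (1.2 mg/dL): 1,200 ÷ 30 = 40 mg/dL.

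**Step 4. Largest accepted ratio over a range of creatinine**

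| Urine creatinine (mg/dL) | Largest UACR if LOQ is 12 mg/dL (mg/g) | Largest UACR if LOQ is 12 mg/L (mg/g) | Albumin equal to 30 mg/g (mg/dL) |
|---|---|---|---|
| 20 | 600 | 60 | 0.6 |
| 40 | 300 | 30 | 1.2 |
| 50 | 240 | 24 | 1.5 |
| 100 | 120 | 12 | 3.0 |
| 200 | 60 | 6 | 6.0 |
| 300 | 40 | 4 | 9.0 |
| 400 | 30 | 3 | 12.0 |

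The last column is 30 × creatinine ÷ 1000. At a creatinine of 100 mg/dL, for instance, the exclusion limit corresponds to 3.0 mg/dL of albumin. With a quantification limit of 12 mg/dL, any albumin above 3.0 and below 12 mg/dL would pass the surrogate with a ratio above the limit.

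**The case against.** The strongest reply is that 12 mg/dL does not trigger anything. The surrogate applies only when the assay cannot quantify the albumin, and the figure is introduced as an example. If the laboratory can measure 5 mg/dL, a ratio can be calculated and exclusion 13 applies in full. This stands: the laboratory's actual limit governs, and the documents do not give it.

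A second reply is that the figure may be a slip for 12 mg/L. That is plausible, and it would remove most of the conflict. It would not remove all of it, since urine with creatinine below 40 mg/dL could still carry a ratio above 30 mg/g. The documents do not say which unit was meant.

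A third reply is that the table shows worst cases. This is also right. The entries are upper bounds for an albumin just under the limit, and many unquantifiable results will be genuinely low.

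Two stronger readings are tempting, and the documents support neither.

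- A reader might infer that the renal exclusion fails. It does not: every quantifiable albumin still yields a ratio that is tested against 30 mg/g, and the separate eGFR exclusion is untouched.
- A reader might infer that new proteinuria on study would be hidden. The section is not limited to Screening, so its scope is unclear. But an acceptable ratio is the language of eligibility, no on-study acceptance limit for UACR is set, and nothing says that an unquantifiable result overrides the investigator's judgement of clinical significance.

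What none of these replies answers is that the sentence decides eligibility, carries only this one figure, and omits the denominator of the criterion it stands in for. No other section supplies the missing condition.

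**Conclusion.** The point holds as a conflict between protocol 12.1.8.2 and exclusion 13. Taken at its printed example, the surrogate guarantees the limit only at a urine creatinine of 400 mg/dL or more. Over the assumed 50 to 300 mg/dL it could accept ratios of up to 240 to 40 mg/g, that is, 8 times (240 ÷ 30) to 1.3 times (40 ÷ 30) the limit. If the unit was meant to be mg/L, the gap is confined to creatinine below 40 mg/dL.

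These sizes rest on the assumed creatinine values and on the example being the real limit of quantification, which cannot be checked from the documents. The text permits enrolment above the limit; it does not show that any such patient was enrolled, or how many might be.

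Severity is minor to moderate. The same eligibility rule applies to every arm before dosing, and the primary efficacy analysis and the sample size are unaffected.

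**What to change.** 1. In protocol 12.1.8.2, replace the example with the laboratory's actual limit of quantification and confirm its unit.
2. Reconcile the surrogate with exclusion 13. One way that keeps the protocol's own threshold is to accept the surrogate only when 1000 × LOQ ÷ measured urine creatinine (both in mg/dL) does not exceed 30 mg/g (3.39 mg/mmol).
3. State whether the surrogate is for Screening only. If it also applies on study, say in the SAP how a ratio that cannot be calculated is reported in the laboratory summaries; SAP section 10.4 has no rule for this.
4. Add a line to protocol 8.3.1. It allows up to two repeats of out-of-range tests within the 45-day screening window, but does not clearly cover an indeterminate result.

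The cost is a few sentences in the protocol and the laboratory instructions. Urine creatinine is already needed to form the ratio, so no new test is added. The downside is that a few patients with dilute screening samples may need a repeat.

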12.1.8.3 Glomerular Filtration Rate (GFR)

Estimated glomerular filtration rate (eGFR) will be calculated according to the Study Operations Manual.

12.1.8.4 Lipids

Fasting lipid assessments will include total cholesterol, high-density lipoprotein (HDL), low-density lipoprotein (LDL), and triglycerides.

12.1.8.5 Coagulation

Coagulation assessments will include prothrombin time (PT), activated partial thromboplastin time (aPTT), international normalized ratio (INR).

12.1.8.6 Antibody Assessments

Blood samples will be collected for assessment of antibody development to pegadricase and uricase and for neutralizing antibodies and anti-pegadricase point of service validation. All blood samples for assessment of antibody development are required to be collected prior to study drug dosing. Antibody samples collected after the screening period will be assessed only in patients in active treatment arms.

12.1.8.7 COVID-19 Testing

Patients with COVID-19 infection can experience a range of clinical manifestations, from no symptoms to critical illness.

Screening Visit:

During Screening, all patients should be tested for COVID-19 by an FDA Emergency Use Authorized COVID-19 molecular assay for detection of SARS-CoV-2 RNA. A patient with a positive test result is permitted to request re-testing. A patient who requests re-testing should wait at least 10 days after the date of the first positive COVID-19 diagnostic test, as long as no symptoms have developed. If the second test is positive for COVID-19, then the patient will be excluded from enrollment. If the second test is negative for COVID-19, then the patient must be tested a third time at least 24 hours after the second test to confirm the negative result.

On Study:

Once a patient is enrolled in the study, the investigational site will manage the patient according to its institutional standards and procedures established for COVID-19. During the study, a patient presenting with both symptoms (only severe and critical illness as per definitions below) of COVID-19 and positive COVID-19 test results will be discontinued from study treatment. The patient will be permitted to resume study visits for continued assessments (but not treatment with SEL-212 or placebo) according to the institutional standards and/or procedures of the investigational site.

Patients with mild-moderate COVID-19 illness (as per definitions below) will be allowed to resume study visits (on treatment with SEL-212 or placebo) after resolution of acute symptoms of clinical disease (except for loss of smell and taste) and meeting quarantine requirements so long as their subsequent dose occurs ≤90 days from their prior dosing day as per section 7.4.1.1. Patients with mild-moderate COVID-19 illness can continue **non-dosing study visits** as per protocol mandated visit window prior to resolution of acute symptoms according to the institutional standards and/or procedures of the investigational site.

Enrolled patients in the study with mild-moderate COVID-19 illness can be treated with anti-SARS-CoV-2 monoclonal antibodies. These patients will be allowed to resume study visits (on treatment with SEL-212 or placebo) after 2 weeks of receiving monoclonal antibodies, and confirmation of resolution of acute symptoms of clinical disease (except for loss of smell and taste), and meeting quarantine requirements so long as their subsequent dose occurs ≤90 days from their prior dosing day as per section 7.4.1.1.

Regardless of COVID-19 disease severity, enrolled patients in the study who are treated for COVID-19 with anti-viral therapy (including Remdesivir), anti-cytokine therapies (including anti-IL-6 or anti-IL-1 therapy), or JAK-inhibitors will be discontinued from study treatment. These patients will be permitted to resume study visits for continued assessments (but not treatment with SEL-212 nor placebo) according to the institutional standards and/or procedures of the investigational site.

The categories of severity of illness (description and criteria) for COVID-19 are noted below as a reference:

Asymptomatic or Pre-symptomatic Infection: Individuals who test positive for COVID-19 but who have no symptoms that are consistent with COVID-19.

Mild Illness: Individuals who have any of the various signs and symptoms of COVID-19 (e.g., fever, cough, sore throat, malaise, headache, muscle pain, nausea, vomiting, diarrhea, loss of taste and smell) but who do not have shortness of breath, dyspnea, or abnormal chest imaging.

Moderate Illness: Individuals who show evidence of lower respiratory disease during clinical assessment or imaging and who have an oxygen saturation (SpO₂) ≥94% on room air at sea level.

Severe Illness: Individuals who have SpO₂ <94% on room air at sea level, a ratio of arterial partial pressure of oxygen to fraction of inspired oxygen (PaO₂/FiO₂) <300 mm Hg, respiratory frequency >30 breaths/min, or lung infiltrates >50%.

Critical Illness: Individuals who have respiratory failure, septic shock, and/or multiple organ dysfunction.

The Investigator will report a patient's positive test results for COVID-19 according to institutional standards and/or procedures.

